- Charlson Comorbidity Index (CCI) score and categories: history of MI, CHF, PVD, CVA/TIA, dementia, chronic pulmonary disease, connective tissue/rheumatic disease, peptic ulcer disease, liver disease, diabetes mellitus, hemiplegia/paraplegia, moderate to severe CKD, local/metastatic malignancy, AIDS/HIV
- Surgical service
- Duration of surgery
- Surgical priority: emergent/urgent vs. elective
- ICU admission preoperatively
- Cardiovascular medications preoperatively: Angiotensin II receptor blockers (ARBs), angiotensin-converting enzyme (ACE) inhibitor, and beta blockers (based on available names extracted from Cerner; may be missing medications that have been held and not restarted in hospital).
- Estimated blood loss
- Use of intraoperative/postoperative vasopressors/inotropes
Yes/no (received anything at all)
Small amount of intraoperative use (phenylephrine (<200 mcg) or ephedrine (<10 mg))
Significant only (i.e. exclude if small doses of phenylephrine (<200 mcg) or ephedrine (<10 mg))
- Laboratory preoperatively (30 days before surgery): NT-proBNP, hemoglobin, creatinine/GFR, troponin
- Respiratory rate
- Postoperative disposition (ward vs. HAU vs. ICU) - multiple entries possible; time of moving in/out of each unit
- Descriptive statistics of troponin as a continuous variable by postoperative days

- Diagnosis of myocardial infarction, MINS, and postoperative myocardial injury
- MINS troponin monitoring
 - o Duration (operative day to the last day of troponin measurement)
 - o Numbers of troponin testing done and frequency
 - o Time of MINS diagnosis (rule in vs. rule out), hours after end of operation as defined by the event of patient leaves the operating room
- Non-MINS causes of troponin elevation
 - o PE/DVT
 - o Sepsis
 - o Rapid atrial fibrillation
 - o Cardioversion < 24 hours
 - o Chronic elevation (excluded)
- Vitals monitoring
 - o Frequency (plot frequency vs. POD)
 - o Duration within POD3
- 30 Day in-hospital mortality

Also, descriptive summaries of the vital statistics as listed in Table 4 will be presented.

Data processing

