Anesthesia	Principal Anesthesia Technique Epidural General Local Monitored Anesthesia care (MAC) / IV Sedation None Regional Spinal Other Unknown	Cohort characteristics
SBP	Systolic blood pressure with time stamp	Potential predictors: univariate vs. multivariate time series; clinician-defined

		predictor variables.
MAP	Mean arterial blood pressure with time stamp	Potential predictors: univariate vs. multivariate time series; clinician-defined predictor variables.
HR	Heart rate/pulse rate with time stamp	Potential predictors: univariate vs. multivariate time series; clinician-defined predictor variables.
RR	Respiratory rate with time stamp	Potential predictors: univariate vs. multivariate time series; clinician-defined predictor variables.
SpO2	Oxygen saturation by pulse oximetry with time stamp	Potential predictors: univariate vs. multivariate time series; clinician-defined predictor variables.
Intraoperative Phenylephrine (>200 mcg)	1/0 Yes/No	Potential predictor Potential confounder
Intraoperative Ephedrine (>10 mg)	1/0 Yes/No	Potential predictor Potential confounder
Intraoperative Norepinephrine	1/0 Yes/No	Potential predictor Potential confounder
Intraoperative Vasopressin	1/0 Yes/No	Potential predictor Potential confounder
Intraoperative Epinephrine	1/0 Yes/No	Potential predictor Potential confounder
Intraoperative Dobutamine	1/0 Yes/No	Potential predictor Potential confounder
Intraoperative Milrinone	1/0 Yes/No	Potential predictor Potential confounder
Time of patient entering room	Time/date	To identify preoperative vitals

Time of patient leaving room	Time/date	To identify postoperative vitals
------------------------------	-----------	----------------------------------

Source: Cerner extraction (please see appendix for details of the CIHI codes)

Variable name	Legend/ICD-10 code	Reason for request
IDN	ID (deidentified)	To deidentify patients in the dataset
MRN	ID	Required for manual chart review of variables that cannot be extracted automatically
Age	Age	Cohort characteristics
Gender	Male vs. Female	Cohort characteristics
Surgical priority	E0: STAT E1: <1 hour E2: <4 hours E2OB: <2 hours E3: <8 - 12 hours E4: <48 hours Elective A dichotomized variable of emergent/urgent vs. elective will be created as a predictor in the primary model	Cohort characteristics
Procedure_code	Cerner procedure code	Cohort characteristics
Procedure_text	The corresponding free text to the Cerner procedure code	Cohort characteristics

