Preoperative ACEI/ARB	Preoperative use (captopril, enalapril, ramipril, perindopril, lisinopril, candesartan, irbesartan, losartan, telmisartan, valsartan, sacubitril/valsartan) 1/0 Yes/No	Potential predictor Potential confounder Note that in order to obtain these variables and due to the limited analytic time from the Cerner team, all medications in the patient's medication administration record that is noted as completed were pulled
Postoperative Phenylephrine (>200mcg)	1/0 Yes/No	Potential predictor Potential confounder
Postoperative Ephedrine (>10mg)	1/0 Yes/No	Potential predictor Potential confounder

Postoperative Norepinephrine	1/0 Yes/No	Potential predictor Potential confounder
Postoperative Vasopressin	1/0 Yes/No	Potential predictor Potential confounder
Postoperative Epinephrine	1/0 Yes/No	Potential predictor Potential confounder
Postoperative Dobutamine	1/0 Yes/No	Potential predictor Potential confounder
Postoperative Milrinone	1/0 Yes/No	Potential predictor Potential confounder
In hospital mortality	1/0 Yes/No	Outcome Cohort characteristic
Start of surgery (time/date) [Enters OR]	Time/date	To define the start of the time series
End of surgery (time/date) [Leaves OR]	Time/date	To define the start of the postoperative time series
Length of OR	Duration in minutes	Potential predictor
PACU length of stay	Duration in minutes (if available, otherwise calculated based on the following two values)	Potential Predictor
Time of PACU admission	Time/date	For time stamps
Time of PACU discharge	Time/date	For time stamps
Time/date of hospital discharge	Time/date	To verify inclusion criteria
Readmission within 3 days of surgery	1/0 Yes/No	Patients who underwent repeat surgery or were readmitted within the first 72 hours postoperatively will be excluded.
Repeat surgery within 3	1/0	Patients who underwent

days of surgery	Yes/No	repeat surgery or were readmitted within the first 72 hours postoperatively will be excluded.
-----------------	--------	---

CIHI – Canadian Institute for Health Information, ICD-10 (International statistical classification of diseases and related problems) codes

References:

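### The phenylephrine and ephedrine flags in the data dictionary cannot yield two of the three vasopressor-use categories planned for the cohort table, and they class an amount exactly at the cut-off differently

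*Combined protocol and SAP*

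**What the plan says.** Under Statistical analysis, Cohort characteristics, use of intraoperative or postoperative vasopressors and inotropes is to be shown overall and by MINS status, in three forms:

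- any use: "Yes/no (received anything at all";
- small use: "Small amount of intraoperative use (phenylephrine (<200 mcg) or ephedrine (<10 mg";
- significant use: "Significant only (i.e. exclude if small doses of phenylephrine (<200 mcg) or ephedrine (<10 mg".

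The Data Dictionary says what will be obtained. In the Surginet table the two drugs named above appear as "Intraoperative Phenylephrine (>200 mcg" and "Intraoperative Ephedrine (>10 mg", each coded 1/0. The Cerner table repeats this for the postoperative period: "Postoperative Phenylephrine (>200mcg" and "Postoperative Ephedrine (>10mg". Neither drug has an amount field or an any-use field in either period. The other five agents (norepinephrine, vasopressin, epinephrine, dobutamine, milrinone) are 1/0 with no cut-off, as in "Intraoperative Norepinephrine".

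**The concern.** The planned table needs to separate three kinds of patient: those given neither drug, those given a little, and those given more. A flag that turns on only above the cut-off merges the first two. If the dictionary is followed as written, the any-use row will count some treated patients as untreated, and the small-use row cannot be filled.

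The boundary symbols also differ. The cohort table uses a strict less-than to define small, and the dictionary uses a strict greater-than to define a positive flag. An amount equal to the cut-off is not small in the first place and not positive in the second.

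At stake is the accuracy of a treatment descriptor shown for MINS against no MINS. Readers will use it to judge how blood pressure was being supported in the two groups.

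**Working it through.** There is no sample-size or power figure to reproduce. The check is whether the three planned categories are determined by the listed fields.

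**Inputs.** Category definitions come from Cohort characteristics, and flag definitions from the Data Dictionary. Small is read as some use that does not reach significant; significant is read as any of the five other agents, or an amount of phenylephrine or ephedrine that is not below its cut-off.

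**Step 1: phenylephrine alone, no other agent.**

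| Amount (mcg) | Cohort-table class | Dictionary flag |
|---|---|---|
| 0 | none | 0 |
| 100 | any use, small | 0 |
| exactly 200 | any use, significant | 0 |
| 300 | any use, significant | 1 |

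Three different classes share the flag value 0. Ephedrine at 0, 5, 10 and 15 mg gives the same pattern.

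**Step 2: all combinations.** Phenylephrine 0/100/200/300 mcg, ephedrine 0/5/10/15 mg, and any other agent yes/no give 4 × 4 × 2 = 32 illustrative profiles. The flags give 2 × 2 × 2 = 8 patterns.

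- In 7 of the 8 patterns at least one flag is positive, and all three categories are determined: any use yes, small no, significant yes.
- The all-zero pattern holds 3 × 3 × 1 = 9 profiles: 1 with no drug, 3 with small use only, and 5 with at least one drug exactly at its cut-off and neither above it. None of the three categories is determined there.

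These are counts of constructed profiles, not of patients.

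**Step 3: what each category becomes.**

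- Any use, built from the flags, is positive only when some flag is positive. It therefore misses patients whose only exposure was phenylephrine and/or ephedrine at or below the cut-off, and it coincides with significant use built from the same flags.
- Small use has no flag pattern of its own and cannot be identified.
- Significant use is recovered except at exactly 200 mcg or 10 mg.

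**Step 4: reach.** The cut-off applies to 2 of 7 agents. A patient who also received any of the other five is correctly counted under any use and significant use.

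**The case against.** The strongest reply is that the dictionary is not a complete list of what will be held. Postoperative GFR is an a priori predictor, yet only preoperative GFR has a row. Diastolic pressure is a planned time series and has no row. A flag above 200 mcg must itself be worked out from an amount, so the 1/0 row may be a derived variable with the dose behind it. The Data sources and Data processing sections also allow chart review for items not retrieved automatically, and the Cerner table records that all completed medications were pulled.

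Part of this stands. It limits the conclusion to what can be derived from the listed fields, and a reader who inferred that the categories can never be produced would go further than the documents do. It does not remove the point. For these drugs the dictionary states a coding rule that conflicts with the planned table, which is more than a missing row. No section assigns vasopressor amounts to chart review. The note on pulled medications sits only in the preoperative beta-blocker and ACEI/ARB rows and does not mention doses.

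It is also fair to say that little depends on these fields. The dictionary tags them as potential predictors and confounders, so a reader might infer that model results are at risk. The documents do not support that. Vasopressors are absent from the non-vital-sign candidate features and from the a priori predictor list. In the secondary and sensitivity list, added predictors are to come from the vital signs data.

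**Conclusion.** The point holds as an internal inconsistency in one descriptive item. From the listed fields, two of the three planned categories (any use and small use) cannot be derived, and the third is ambiguous at the exact cut-off. The loss is confined to patients whose only exposure was phenylephrine and/or ephedrine at or below the cut-off. It would be wrong to extend it to vasopressors in general, because five of the seven agents are recorded at any use.

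The number of patients affected is unknown. The documents give no rates of use for either drug, so any count would rest on a guess. The primary model and the specified secondary models are untouched. The conclusion assumes that the dictionary rows are the fields that will reach the analyst; if amounts are in fact held, only the boundary mismatch and the missing documentation remain. This is a minor point, worth correcting because the correction is small.

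**What to change.** Request the total administered amount of phenylephrine and of ephedrine, intraoperatively and postoperatively, and derive the cohort-table categories from it, keeping the small category intraoperative as planned. If amounts cannot be supplied, add an any-use flag beside each existing flag. Small use is then any use with a negative cut-off flag, provided the boundary in the cohort table is made to match the flag.

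In either case, reconcile the less-than and greater-than signs between Cohort characteristics and the two dictionary tables so that each amount falls in exactly one category. Which cut-off to use, and on which side the boundary value falls, is for the investigators. If the amounts are already available through chart review or the medication pull, it is enough to say so and name the source.

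The cost is a small change to the extraction request for two drugs and a line of wording. The Cerner table notes limited analytic time from that team, which favours settling this in one request.
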